3.4.2 Other Adverse Events

The number and percentage of patients by treatment group, SOC and PT will be presented for the following:

- Any AEs
- Any TEAEs (overall and by maximum severity)
- Any TEAEs with CTCAE Grade ≥ 3
- Any study drug related TEAEs (overall and by maximum severity)
- Any TEAEs leading to discontinuation of study drug
- Any TEAEs leading to discontinuation of study
- Any AEs leading to death

The AEs described above will be summarized separately by system organ class and preferred term. Listings will be presented specifically for SAEs and TEAEs leading to discontinuation of study drug.

3.4.3 Clinical Laboratory Tests

Clinical laboratory evaluations (including serum chemistry, hematology, endocrinology/thyroid function, and urinalysis) will be obtained as indicated in Table 2 Schedule of Procedures in the protocol and processed by a central laboratory. A list of laboratory tests to be performed are included in Appendix B in the protocol.

Laboratory values and changes from baseline will be presented at each visit and baseline by laboratory test. In addition, the number and percentage of patients with parameters outside the normal range (below the lower limit of normal ($<LLN$) or above the upper limit of normal ($>ULN$)) will be presented by visit and treatment group. The count and percentage of patients with clinically significant changes will be tabulated by treatment group. Clinically significant changes will be identified as any TEAEs related to significant change in laboratory test. Medical review of AE will be performed by Medpace to identify any clinically significant changes. The provided classifications will be used in analysis.

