1.3.2 Nonclinical Safety

Safety pharmacology studies revealed no effects related to central nervous system or respiratory function. In dogs, transient QTc prolongation was observed at 100 mg/kg/day and above, whereas no other findings related to cardiac function were reported.

A comprehensive repeated dose toxicology program has been conducted in rats and dogs. In rats dosed up to the limit dose of 1 g/kg/day, no relevant setanaxib-related toxicities were identified in any of the studies, whereas the no-observed-adverse-effect-level (NOAEL) was established at 150 mg/kg/day in the 26-week dog study and 300 mg/kg/day in the pivotal 39-week dog study. Treatment-related findings in the dog included electrocardiogram (ECG) (QT-prolongation) and effects on the erythrocyte and reticulocyte counts indicative of effects on bone marrow. Reductions in red blood cell parameters were observed in dogs exposed to high dose levels of setanaxib (≥ 500 mg/kg/day) after a few weeks of treatment. The affected dogs showed minimal (10% to 20%) red blood cell reductions, occasionally with a concomitant increase in hematopoiesis in the spleen and/or bone marrow, followed by a marked increase in circulating reticulocytes, and subsequent recovery towards normal levels. One female developed non-regenerative anemia and was euthanized. Apart from this female, dogs that were affected at high exposures generally tended

to recover following a dose reduction or upon cessation of dosing. Slight to moderate follicular cell hypertrophy of the thyroid was observed in some dogs of the 28-day and 13-week study, but no such change was observed in the 26- and 39-week studies despite comparable exposures. Hormone analysis of thyroid-stimulating hormone (TSH) and thyroxine (T4) revealed indications of low total T4 and high TSH levels in individual high dose animals sometimes correlating with the hypertrophy. Setanaxib has been investigated in a standard battery of mutagenicity tests and was found not genotoxic.

Rat and rabbit studies addressing fertility, early embryonic- and embryo-fetal development have been conducted. There was no evidence of any embryo-fetal toxicity, except for a lower mean fetal weight at the dose level of 1000 mg/kg/day in rats. No treatment-related malformations have been observed. In addition, sperm parameters have been found unaffected by setanaxib treatment. For further details, refer to the IB.

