3.1 Summary of Study Design

This is a randomized, double-blind, placebo-controlled Phase 2a study assessing oral setanaxib in patients with Alport syndrome. The safety, tolerability, PK, PD, and preliminary efficacy of setanaxib will be assessed over 24 weeks of treatment. The study design is outlined in [Figure 1](#). The inclusion and exclusion criteria are designed to enroll a population of patients with Alport syndrome at risk of disease progression. In the EU, only adult patients (aged 18 to 50 years, inclusive) will be enrolled. Patients are required to have persistent proteinuria (UPCR ≥ 90 mg/mmol [0.8 g/g]) despite treatment with a stable dose of RAS inhibitor therapy (ACEis and/or angiotensin II type I receptor blocker [ARBs]) at the maximum allowed dose or maximum-tolerated daily dose for at least 8 weeks prior to consent/assent. A stable dose is defined as a dose within 25% of the dose at randomization. Patients should remain on their regimens of RAS inhibitors for the whole duration of the study. Patients with proven intolerance to ACEi and ARB are allowed in the study. This study aims to assess the safety of setanaxib as an add-on treatment to current RAS inhibitor treatment, in patients with Alport syndrome at risk of disease progression and with limited treatment options available. The double-blind, placebo-controlled design is chosen to provide safety data and preliminary efficacy for setanaxib in addition to the standard of care treatment in this patient population with a standard of care (with placebo) arm as reference. This will help to guide the design of further Phase 2/3 studies of setanaxib in Alport syndrome.

Patients must have UPCR ≥ 90 mg/mmol [0.8 g/g] at 2 consecutive measurements during Screening, separated by at least 2 weeks and calculated by the central laboratory. The baseline measurement will be the geometric mean of these 2 measurements. Patient must also have eGFR ≥ 30 mL/min/1.73 m² at Study Visit 1 or 2, calculated at the central laboratory using the Chronic Kidney Disease Epidemiology Collaboration formula (CKD-EPI) for patients ≥ 18 years of age and the revised bedside Schwartz formula for patients 12 to 17 years of age.

Eligible patients will be randomized in a 2:1 ratio to receive either setanaxib or placebo for 24 weeks, in addition to their stable dose of RAS inhibitor therapy, with setanaxib dosing based on age. In the EU, the setanaxib dose will be 1600 mg/day, as only adult patients will be enrolled.

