4.3 Withdrawal Criteria

A patient may prematurely discontinue study drug and/or withdraw from the study at any time. A distinction must be made between premature discontinuation of study drug and withdrawal from the study. A patient may prematurely discontinue study drug and still continue his/her participation in the study.

The reasons for premature discontinuation of study drug and for withdrawal from the study must be documented in the eCRF. Reasons for premature discontinuation of study drug include, but are not limited to, the following:

- Withdrawal of consent/assent;
- Any event, laboratory abnormality, intercurrent illness, or other medical condition that indicates to the Investigator that continued participation is not in the best interest of the patient;
- Pregnancy;
- Patient failure to comply with Protocol requirements or study-related procedures;
- Termination of the study by the Sponsor or regulatory authority;

- Initiation of medications known to be potent CYP3A4 inhibitors (itraconazole, lopinavir/ritonavir, telaprevir, clarithromycin, ritonavir, ketoconazole, indinavir/ritonavir, conivaptan, and voriconazole), potent CYP3A4 inducers (avasimibe, carbamazepine, enzalutamide, mitotane, nevirapine, phenobarbital, phenytoin, rifabutin, rifampicin, rifapentine, and St John's wort), or potent UGT1A9 inhibitors and inducers (mefenamic acid and rifampicin);
- The patient experiences mean QT prolongation (mean QTcF interval >500 milliseconds AND increase by >60 milliseconds over the mean baseline QTcF);
- Severe allergic reactions to the study drug;
- The patient has CTCAE Grade ≥ 2 anemia AND the retest absolute reticulocyte count is below 50% of the baseline value. In this case, study drug will not be resumed and will be permanently discontinued; or
- The patient has suspected DILI meeting [Criterion 3](#) in [Appendix C](#).

Unless a patient withdraws his/her consent/assent to participate in the study, all patients should be encouraged to complete the remaining study visits, regardless of whether they are still receiving study drug.

For patients who are withdrawn from the study prior to completion of Study Visit 8, the Early Termination Visit procedures will be completed, if possible, at the time the decision is made to withdraw the patient. The Early Termination Visit will consist of all of the Study Visit 8 procedures. The reason for patient withdrawal must be documented in the eCRF.

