9.2.3 Sample Size Determination

The sample size of approximately 18 patients is considered sufficient to provide an initial assessment of setanaxib versus placebo in Alport syndrome. Withdrawn patients may be replaced, unless withdrawn for a reason related to safety, as per the judgment of the Investigator. A maximum of 20 patients will be randomized for the study. The study sample size was chosen empirically, and no formal statistical hypothesis will be tested.

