3.4.1 Adverse Events -Primary Endpoint

The primary endpoints are:

- Percentage of patients with treatment-emergent SAEs;
- Percentage of patients with treatment-emergent AESIs.

All adverse events (AEs) will be coded to SOC and PT using MedDRA version v 26.1. Treatment-emergent adverse events (TEAEs) are defined as AEs that start after the first dose of study drug and up to 30 days post-last dose of study drug. Pre-treatment AEs are defined as AEs that started prior the first dose of study drug and post-treatment AEs are defined AEs that started more than 30 days after last dose of study drug.

AESI is defined as CTCAE Grade ≥ 2 anemia, defined as hemoglobin <10g/dL, and absolute reticulocyte counts of <50% of the baseline value (Screening Study Visit 2), which are confirmed by repeat testing.

Estimand

To assess the primary endpoint for treatment-emergent SAE, the safety estimand is defined by the following key attributes, according to the framework provided in International council for Harmonization (ICH) E9 (R1) [1]:

- **Treatment:** Setanaxib treated patients compared to placebo
- **Population:** The SAS comprised of all randomized patients who took at least 1 dose of the study drug.
- **Variable of interest:** Treatment-emergent SAEs
- **Intercurrent event handling:** All events will be counted regardless of early discontinuation of treatment, up to 30 days post-last dose of study drug
- **Summary measures:** Count and percentage of patients experiencing SAEs during the Treatment Period up to 30 days post-final dose.

The number and percentage of patients with SAEs will be presented by treatment group, system organ class (SOC), and preferred term (PT). Similar summaries will be presented for treatment emergent AESIs. The number and percentage of patients with study drug related treatment-emergent SAEs and AESIs will be presented by treatment group, SOC and PT.

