3.4.5 Electrocardiograms

A standard 12-lead ECG will be performed at timepoints specified in Table 2 Schedule of Procedures in the protocol. Continuous ECG parameters will be summarized with descriptive statistics by treatment group for each visit. The number and percentage of patients with clinically significant changes will be tabulated by treatment group. In addition, a summary of QTcF measurements will be summarized by treatment group for the following predefined criterion:

- QTcF > 450 for male

- QTcF>470 for female.

QTcF will be calculated according to the following formula:

$$QTcF = \frac{QT}{\sqrt[3]{RR/1000}}$$

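### By-visit laboratory, vital-sign and ECG tables mix on-drug and off-drug values, so they cannot separate adaptation on setanaxib from recovery after stopping it

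*SAP*

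**What the plan says.** For laboratory tests, SAP 3.4.3 states: "Laboratory values and changes from baseline will be presented at each visit and baseline by laboratory test". It also counts patients outside the normal range by visit and group. SAP 3.4.4 summarises vital signs and their changes by visit. SAP 3.4.5 states: "Continuous ECG parameters will be summarized with descriptive statistics by treatment group for each visit".

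None of these sections refers to dosing status. Nor do the general rules:
- The Safety Analysis Set (SAP 3.2.2) is anyone randomised who took at least one dose.
- SAP 3.1.8 uses whatever safety data exist, without imputation.
- SAP 3.1.2 assigns measurements to visits by the CRF visit or by day counted from first dose. A scheduled value takes precedence over an unscheduled one in the same window.

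Protocol 4.3 says that, unless consent is withdrawn, "all patients should be encouraged to complete the remaining study visits, regardless of whether they are still receiving study drug".

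A dosing window exists for adverse events only. SAP 3.4.1 counts events as treatment-emergent up to 30 days after the last dose, and "post-treatment AEs are defined AEs that started more than 30 days after last dose of study drug".

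**The concern.** Some of the reasons for stopping drug are the toxicities that these tables track. Protocol 8.8.1 interrupts drug for Grade 2 or higher anaemia and ends it if the reticulocyte retest is low. Protocol 4.3 lists QTcF prolongation as a reason to stop. Appendix C stops drug under Criterion 3. A patient stopped for one of these reasons who keeps attending, and whose values recover, then contributes recovering off-drug values to the later setanaxib rows.

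The protocol's own dog data make the distinction matter. Protocol 1.3.2 describes red-cell reductions followed by a reticulocyte rise and a return towards normal, without tying that recovery to stopping. It also reports that affected dogs generally tended to "recover following a dose reduction or upon cessation of dosing". Whether a fall in haemoglobin resolves on drug or only off drug is therefore an open question about setanaxib. A reader of the by-visit tables would look there for the answer and could not find it.

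**Working it through.** The plan gives no figure to reproduce. The sample size is empirical: "The study sample size was chosen empirically, and no formal statistical hypothesis will be tested". The check is arithmetic on the tabulation rule.

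**Inputs from the documents**
- About 18 patients (Protocol 9.2.3).
- Allocation: "Eligible patients will be randomized in a 2:1 ratio to receive either setanaxib or placebo for 24 weeks". Expected setanaxib patients: 18 × 2/3 = 12.
- Post-baseline visits at Weeks 2, 6, 12, 18, 24 and 28 (Protocol Appendix A).

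**Assumed inputs (not in the documents)**
- Number k of setanaxib patients stopped for toxicity: 1 to 3.
- Haemoglobin fall d in those patients: 2 to 4 g/dL.
- They recover and keep attending.

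**Step 1. Share of a row.** k/12 gives 1/12 = 8%, 2/12 = 17%, 3/12 = 25%. If all patients shared one on-drug effect, k fully recovered off-drug patients would shrink the pooled mean by the same fraction.

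**Step 2. Can the table tell the two explanations apart?** Take k = 2, d = 3, the other ten patients unchanged, and mean changes at Weeks 2, 6, 12, 18, 24.
- A: two patients fall at Week 6 and adapt while still on drug. Week 6 mean = 2 × (−3)/12 = −0.50. Row: 0, −0.50, 0, 0, 0; n = 12 throughout.
- B: two patients fall at Week 6, are stopped, and recover off drug. Row: 0, −0.50, 0, 0, 0; n = 12 throughout.

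The rows are identical, and they are identical for every combination of k = 1 to 3 and d = 2, 3 or 4 g/dL.

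**Step 3. Apparent recovery, with a smaller effect in the other patients.** Assume 2 of 12 stop at Week 6 at −3.0 g/dL and recover fully, while the other 10 stay at −0.8.
- Week 6: (10 × −0.8 + 2 × −3.0)/12 = −14/12 = −1.17.
- Week 24 as planned: (10 × −0.8 + 2 × 0)/12 = −0.67. Apparent recovery: 1 − 0.67/1.17 = 43%.
- Week 24 if the two recover only halfway: (−8 − 3)/12 = −0.92. Apparent recovery: 1 − 0.92/1.17 = 21%.

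**Step 4. Does an on-treatment-only mean cure it?** Week 24 with the two removed: −8/10 = −0.80. Apparent recovery: 1 − 0.80/1.17 = 31%. Most of the drift remains, because the affected patients have left. In scenario B the on-treatment-only means equal the pooled ones, and only n changes, from 12 to 10.

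**Step 5. What keeps the signal?** In Step 3, the last on-treatment value over all 12 patients averages −1.17. In scenario B, the worst on-treatment value averages −0.50, with 2 of 12 patients ever affected. The two rows differ when a patient is interrupted and later resumes, which Protocol 8.8.1 allows: the last on-treatment value may then be a recovered one, and only the worst value records the low.

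**Step 6. How likely is such a patient?** 1 − (1 − p)^12 for assumed toxicity-stop rates p of 5%, 10% and 20% gives 46%, 72% and 93% for at least one among 12.

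**The case against.** The strongest reply is that by-visit means are not the safety endpoints. The primary endpoint counts patients with treatment-emergent SAEs and AESIs. The laboratory endpoint is identified from treatment-emergent events, so it already carries the 30-day window, and later recovery cannot remove a patient from it. SAP 3.4.2 tabulates and lists events leading to discontinuation of study drug, SAP 3.4.5 adds a QTcF threshold summary by group, and SAP 7 lists all patient data. With about 12 setanaxib patients those listings can be read case by case. The SAP is also silent on pooling rather than prescribing it, and the separate programming specifications could add a flag. Protocol 1.4.2 reports no haematopoietic, thyroid or cardiovascular signal in completed studies.

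All of this stands, and it limits the point. A reader might infer that toxicity would be hidden or that the report as a whole would understate harm. The documents do not support that: an affected patient still appears in the event tables and listings, and a fall seen at a scheduled visit still shows at that visit. Three narrower readings also go too far.
- Stopping does not cover every liver case, because drug may continue under Appendix C Criteria 1 and 2 subject to listed exceptions.
- Protocol 4.3 lists no vital-sign-specific reason to stop, so for vital signs there is mixing but no evident selection by toxicity.
- The half-life of about 8 to 14 hours (Protocol 1.4.1) describes plasma drug. It does not say how long an effect on haemoglobin or ALT lasts.

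What the reply does not do is repair the by-visit time course. No worst-value or shift table is named. The precedence rule in SAP 3.1.2 can also drop unscheduled retests from these tables, and nothing commits the programming specifications to a flag.

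**Conclusion.** The point holds for the interpretation of secondary descriptive tables. As written, off-drug values enter the setanaxib rows of the laboratory, vital-sign and ECG summaries, and those rows cannot distinguish adaptation on drug from recovery after stopping. One to three patients off drug would be 8% to 25% of a row of 12. The 43% apparent recovery is an illustration that rests on an assumed stop rate, size of fall, full recovery and continued attendance, none of which the documents give. If nobody stops or is interrupted during treatment, only the follow-up visit is off drug and the treatment-period rows are unaffected.

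A reader might also conclude that restricting the tables to on-treatment values would solve the problem. It would not: in the same illustration the on-treatment mean still appears to recover by 31%.

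**What to change.** Keep the planned by-visit tables and add the following to SAP 3.4.3 to 3.4.5.

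1. **Flag.** Classify each value as on- or off-treatment from the last dose date, and from interruption dates if the CRF records them. State a post-dose lag, fixed before unblinding. It should be at least 7 days, so that the retest made within 7 days of an interruption counts as on-treatment. Re-using the 30-day event window would not work, because the Week 28 visit falls nominally 28 days after Week 24 and would then count as on-treatment.
2. **Counts.** Show the on-treatment n at each visit beside the total n.
3. **Per-patient rows.** Add worst on-treatment and last on-treatment values with change from baseline for haemoglobin, reticulocytes, ALT, AST, bilirubin and QTcF. Draw them from all values, including unscheduled ones, and state the direction of worst: lowest for haemoglobin and reticulocytes, highest for the others.
4. **Labels.** Mark Week 28 and any other value beyond the lag as off-treatment.
5. **Reading rule.** Do not rely on an on-treatment-only by-visit mean as evidence of recovery.

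The cost is SAP wording, one derived flag, a few table rows and smaller on-treatment n at later visits. Trial conduct and the clinical stopping rules are untouched. SAP 3.3.7 already uses first and last dose dates, so permanent stops can be flagged. The documents do not show that interruption dates are recorded, and the sponsor should check. If they are not, the worst on-treatment row still captures the low.

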12. Has a history of aplastic anemia, or any current marked anemia, defined as hemoglobin <10.0 g/dL;
13. Has uncontrolled hypothyroidism. Patients with subclinical hypothyroidism may be included. Subclinical hypothyroidism is defined biochemically as a normal serum free T4 concentration in the presence of an elevated serum TSH concentration;

14. Has any laboratory abnormality or condition that, in the opinion of the Investigator, could interfere with or compromise a patient's treatment, assessment, or compliance with the Protocol and/or study procedures;
15. Has any other condition that, in the opinion of the Investigator, constitutes a risk or contraindication for the participation of the patient in the study, or that could interfere with the study objectives, conduct, or evaluation;
16. Uses medications known to be potent CYP3A4 inhibitors (itraconazole, lopinavir/ritonavir, telaprevir, clarithromycin, ritonavir, ketoconazole, indinavir/ritonavir, conivaptan, and voriconazole), potent CYP3A4 inducers (avasimibe, carbamazepine, enzalutamide, mitotane, nevirapine, phenobarbital, phenytoin, rifabutin, rifampicin, rifapentine, and St John's wort), or potent UGT1A9 inhibitors and inducers (mefenamic acid and rifampicin) within 21 days prior to study drug administration;
17. Has known psychiatric illness/social situations that would limit compliance with study requirements, substantially increase risk of incurring AEs, or compromise the ability of the patient to give written informed consent/assent;
18. Has known hypersensitivity or intolerance to setanaxib or to any of its excipients;
19. Has a history of chronic liver disease (eg, PBC, alcoholic liver disease, chronic viral hepatitis including hepatitis B and C, non-alcoholic fatty liver disease, and hemochromatosis);
20. Has plasma alanine aminotransferase (ALT) and/or aspartate aminotransferase (AST) $>3 \times$ the upper limit of normal (ULN) at Study Visit 1 or 2 (Screening);
21. Has total bilirubin $>2 \times$ ULN at Study Visit 1 or 2 (Screening); or
22. Has international normalized ratio >1.2 at Study Visit 1 or 2 (Screening) (criterion not applicable for patients on anticoagulant therapy).

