APPENDIX C: DETECTION AND MANAGEMENT OF SUSPECTED OR CONFIRMED CASES OF DRUG-INDUCED LIVER INJURY

Particular attention will be given to the detection and management of suspected or confirmed cases of drug-induced liver injury (DILI). If any of the following laboratory results or clinical signs or symptoms are obtained during the study, the Investigator will instruct the patient to return to the study center within 48 hours of receipt of the laboratory test results to undergo a retest:

- Aspartate aminotransferase (AST) or alanine aminotransferase (ALT) $\geq 3 \times$ the upper limit of normal (ULN);
- AST or ALT $> 2 \times$ Baseline;
- Total bilirubin $> 2 \times$ ULN; or
- Clinical signs or symptoms that are, in the opinion of the Investigator, consistent with hepatitis (such as right upper quadrant discomfort, fever, fatigue, nausea, vomiting, jaundice, rash, or eosinophilia $> 5\%$) or drug-induced hepatotoxicity. Isolated eosinophilia $> 5\%$ without clinical signs or symptoms that are consistent with hepatitis or hepatotoxicity by the Investigator's medical judgment, should not be considered suspected DILI. Retesting of eosinophilia ($> 5\%$) will only be required in case this is observed in combination with at least 1 of the other criteria listed above.

Baseline values for liver tests (ALT, AST, and total bilirubin) are determined by averaging the values obtained at Screening Visits 1 and 2 to obtain the arithmetic mean.

The results of the test and retest will be reviewed to determine if they meet Criteria 1, 2, or 3, as outlined below.

Criteria for Close Monitoring of Liver Biochemistry and IMP Action

Criteria for close monitoring of liver biochemistry and investigational medicinal product (IMP) action include the following:

1. For patients with **Baseline ALT and/or AST $< \text{ULN}$** , unless an alternative cause for the laboratory abnormalities is immediately apparent in the opinion of the Investigator and documented at the time of the laboratory test elevations, close monitoring for suspected DILI will be performed in patients with any of the following criteria confirmed by repeat testing:
 - a. ALT or AST $> 3 \times$ ULN;
 - b. Total bilirubin $> 2 \times$ ULN;
 - c. International normalized ratio (INR) > 1.5 (except for patients on anticoagulant therapy); or

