 - d. Clinical signs or symptoms that are, in the opinion of the Investigator, consistent with hepatitis (such as right upper quadrant discomfort, fever, fatigue, nausea, vomiting, jaundice, rash, or eosinophilia $> 5\%$) provided the latter is in combination with any of the other criteria listed under Criterion 1).
2. For patients with **Baseline ALT and/or AST between $\geq \text{ULN}$ and $< 3 \times \text{ULN}$** , unless an alternative cause for the laboratory abnormalities is immediately apparent in the opinion of the

Investigator and documented at the time of the laboratory test elevations, close observation for suspected DILI will be performed in patients with any of the following criteria confirmed by repeat testing:

- a. ALT or AST $>2 \times$ Baseline at any time;
- b. Total bilirubin $>2 \times$ ULN;
- c. INR >1.5 (except for patients on anticoagulant therapy); or
- d. Clinical signs or symptoms that are, in the opinion of the Investigator, consistent with hepatitis (such as right upper quadrant discomfort, fever, fatigue, nausea, vomiting, jaundice, rash, or eosinophilia $>5\%$ provided the latter is in combination with any of the other criteria listed under [Criterion 2](#)).

During the close monitoring period in [Criteria 1](#) or 2, IMP can be continued, unless any of the following occur:

- The patient is symptomatic in addition to having elevated laboratory parameters;
 - Close monitoring is not possible;
 - Criterion 3 (see below) are met and no other cause for laboratory abnormalities is clinically apparent and documented by the Investigator in the study documents; or
 - At the discretion of the Investigator.
3. **For patients meeting any of the following events**, IMP will be discontinued when no other cause for the laboratory abnormalities is immediately apparent:
- a. ALT or AST $>5 \times$ Baseline;
 - b. ALT or AST $>10 \times$ ULN;
 - c. ALT or AST $>3 \times$ Baseline with 1 or more of the following; or
 - Total bilirubin $>2 \times$ ULN;
 - Total bilirubin $>1.5 \times$ Baseline and $>ULN$;
 - INR >1.5 (except for patients on anticoagulant therapy); or
 - Clinical signs or symptoms that are, in the opinion of the Investigator, consistent with drug-induced hepatotoxicity.
 - d. ALT or AST $>$ Baseline with any 2 or more of the following:
 - Total bilirubin $>2 \times$ ULN or $1.5 \times$ Baseline;
 - INR >1.5 (except for patients on anticoagulant therapy); or

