3.1.2 Analysis Visits

Scheduled visits will be assigned to analysis visits as recorded on the Case Report Form (CRF). Unscheduled and early termination (ET) visits will be assigned to analysis visits according to the following visit windows:

Analysis Visit	Target Analysis Day	Low Analysis Day	High Analysis Day
Day 1 (Visit 3)	1	NA	NA
Week 2 (Visit 4)	15	2	29
Week 6 (Visit 5)	43	30	64
Week 12 (Visit 6)	85	65	106
Week 18 (Visit 7)	127	107	148
Week 24 (EOT) (Visit 8)	169	149	183
Week 28 (Safety FUP)	197	184	197+

For each analysis visit, if a scheduled visit occurs within the analysis day window, then the measurement from this scheduled visit will be used as the measurement for the analysis visit. If no scheduled visit occurs within the analysis day window, the unscheduled measurement closest to the target day will be used. If measurements are equidistant to the target day, the latter will be used. If no visits occur within the analysis day window, the measurement for this analysis visit will be treated as missing.

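### Cheap improvement, low weight: no value-based laboratory summary shows by arm who worsened from baseline, and by-visit tables omit a worse unscheduled value when a scheduled one shares its window

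*SAP*

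**What the plan says.** SAP 3.4.3 plans three laboratory summaries: values and change from baseline at each visit; "the number and percentage of patients with parameters outside the normal range" (below LLN or above ULN) by visit and arm; and clinically significant changes by arm, identified through TEAEs and medical review. Neither document specifies a shift table or a worst post-baseline value.

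SAP 3.1.2 decides which value represents a visit: "if a scheduled visit occurs within the analysis day window, then the measurement from this scheduled visit will be used". Failing that, the unscheduled value closest to the target day is taken. The worst value is never the criterion.

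Protocol 4.2 lets patients enter with abnormal results. "Patients with subclinical hypothyroidism may be included" (raised TSH, normal free T4). Anemia is excluded only as a history of aplastic anemia or "any current marked anemia, defined as hemoglobin <10.0 g/dL". ALT/AST is excluded only above 3 × ULN and total bilirubin only above 2 × ULN.

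The protocol also generates unscheduled samples when toxicity is suspected. Section 8.8.1 calls for a reticulocyte retest within 7 days after Grade 2 or worse anemia. Appendix C has the patient "return to the study center within 48 hours of receipt of the laboratory test results to undergo a retest", then monitors liver tests 2 or 3 times a week.

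**The concern.** Safety is the primary objective, and Protocol 1.6.2 names thyroid, anemia and liver risks because of toxicology findings and ongoing clinical studies. For these tests the useful summary is how many patients in each arm became abnormal, or became worse, on treatment.

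The planned value-based tables do not give that, for two reasons. An abnormality present at entry and one that arises on treatment both count as out of range at a visit. And the samples taken because a problem is suspected are the ones that give way to the scheduled value, so a peak between visits can be missing from the by-visit counts and from the minimum and maximum of change from baseline.

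At stake is a clear reading of small laboratory shifts in a trial meant to guide Phase 2/3 design.

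**Working it through.** The sample size was chosen empirically (Protocol 9.2.3) and the plan gives no figure on this point to reproduce. The check applies the SAP's own rules.

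**1. Entry and on-treatment abnormality.** Inputs: about 18 patients at 2:1, so 12 v 6. The number entering with an abnormal value is not given, so the weight is per patient: 1/12 = 8.3 points (setanaxib) or 1/6 = 16.7 points (placebo) at each visit where the abnormality persists, the same as one new case.

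By-visit totals do not identify who moved. With N patients in an arm, b abnormal at baseline and v at a visit, the number newly abnormal at that visit lies between max(0, v − b) and min(v, N − b). Illustration with assumed counts N = 12, b = 4, v = 4: from max(0, 0) = 0 to min(4, 8) = 4.

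Worsening within the abnormal range is also invisible in this table. With baseline ALT at 2 × ULN, Appendix C Criterion 2a ("ALT or AST $>2 \times$ Baseline at any time") is crossed above 2 × 2 = 4 × ULN. The patient is a single above-ULN count both before and after.

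**2. Retests and close monitoring.** Target days and windows are from SAP 3.1.2; allowed deviations are from Protocol Appendix A.

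| Visit | Target | Allowed | Latest on-time day | Window end | Days left | Latest + 7 |
|---|---|---|---|---|---|---|
| Week 2 | 15 | ±3 | 18 | 29 | 11 | 25 |
| Week 6 | 43 | ±7 | 50 | 64 | 14 | 57 |
| Week 12 | 85 | ±7 | 92 | 106 | 14 | 99 |
| Week 18 | 127 | ±7 | 134 | 148 | 14 | 141 |
| Week 24 | 169 | ±7 | 176 | 183 | 7 | 183 |

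A repeat sample up to 7 days after an on-time visit always shares that visit's window, so it is not tabulated. The tightest case is Week 24. There, a 48-hour liver retest stays in the window if results arrive within 7 − 2 = 5 days (turnaround is an assumption).

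From an on-target visit to the window end, close monitoring gives 2 weeks × 2 to 3 = 4 to 6 samples (Weeks 2 and 24) or 3 weeks × 2 to 3 = 6 to 9 samples (Weeks 6, 12 and 18). None is tabulated.

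**3. ET visits.** An ET value is set aside on days after the scheduled visit but inside the same window (Weeks 2, 6, 12 and 18). The denominator is every day from Day 2 to the day before Visit 8.

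- On target (Visit 8 on Day 169): 14 + 21 + 21 + 21 = 77 of 167 days = 46%.
- All latest (Day 176): 11 + 14 + 14 + 14 = 53 of 174 = 30%.
- All earliest (Day 162): 17 + 28 + 28 + 28 = 101 of 160 = 63%.

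On the remaining days before the next scheduled visit, the ET value is used for that visit.

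**The case against.** The strongest reply is that the protocol's laboratory endpoint is clinically significant change, and SAP 3.4.3 tabulates exactly that by arm. SAP 3.4.2 adds TEAEs by arm, preferred term and maximum severity. These counts are per patient, treatment-emergent and not bound by the visit windows, and Protocol 8.1 makes a pre-existing condition an AE only if it changes. A worse retest or ET value reported as an AE is therefore counted. This stands. A reader might infer that the plan gives no by-arm percentage of treatment-emergent laboratory abnormality at all; the documents do not support that.

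Other parts of the reply also stand:

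- SAP 3.4.3 does not rule out a baseline row in the out-of-range table. It would show entry abnormality separately, though not which patients moved.
- The scheduled value that triggers a retest is normally kept, so the ALT example would usually appear in change from baseline and its maximum. What is left out is a later, worse value.
- The anemia AESI is counted as an AE even though the confirming reticulocyte count is usually unscheduled.
- A reported suspected DILI brings an unblinded ad-hoc IDMC review and an enrollment pause (Protocol 8.8.2), so patients do not depend on these tables for protection.
- Patients who only stop study drug are encouraged to keep attending (Protocol 4.3), so ET need not follow from stopping treatment.
- SAP 7 lists all available data, and about 18 patients can be read by eye.

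What the reply does not cover is a new or worsened value that nobody reports as an AE, and the size of a peak between visits. Reporting rests on investigator judgment (Protocol 8.1), and the by-visit minimum and maximum follow the same selection rule.

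**Conclusion.** The point holds as a reporting gap of low weight. No value-based by-arm summary shows movement from normal to abnormal or worsening from an abnormal baseline, and a worse unscheduled or ET value is left out of the by-visit tables whenever a scheduled value lies in its window. No planned estimate is wrong and no data are lost.

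The size rests on assumptions. The point values in step 1 assume a 12 v 6 split and are per patient, because the number entering abnormal is unknown. The ET percentages count calendar days under on-time visits; they do not predict how many ET visits will occur or be set aside.

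A reader might also infer that a worst-value table could stand in for the suspected-DILI criteria. It could not: Appendix C Criteria 1 and 2 need repeat confirmation and no immediately apparent alternative cause, and they include INR and symptoms.

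**What to change.** Add to SAP 3.4.3, before unblinding, by-arm shift tables from baseline to worst post-baseline value, using all scheduled, unscheduled, retest and ET results:

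- **Thyroid:** TSH and free T4 status classified jointly from the same sample.
- **Red cells:** hemoglobin category including below 10 g/dL, and reticulocytes below 50% of the Screening Visit 2 value.
- **Liver:** ALT, AST and total bilirubin by multiples of ULN and of baseline, at the numeric thresholds in Appendix C. Classify each analyte on its own baseline as defined in SAP 3.1.3, which avoids placing a patient with discordant ALT and AST under two rules. Label these as laboratory threshold crossings, not suspected DILI, and show whether each was confirmed on repeat testing.

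Show the number of samples per patient, because retested patients have more chances of an extreme value. Keep the TEAE-based count and the by-visit tables.

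The cost is SAP wording and shells for three groups of tables, with no new data.
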